7. SAMPLE SIZE AND FEASIBILITY

7.1 Sample size sought

The aim is to recruit about 6,500 people to the trial. This is based on a wish to identify a reduction of one fewer person per hundred allocated an active treatment sustaining a fracture each year over a median period of three years, if this was the true effect. Based on data from published trials in similar contexts the anticipated all fracture rate in the control groups is 15%. A total of 4000 participants would be needed in the analysis to have 80% power (2P<0.05) to detect an overall reduction to 12%. If the true effect is somewhat larger, say a 4% absolute benefit, the power will be over 90%. A trial of this size also has over 80% power to identify a 2% absolute difference in hip fracture rates (from 6% to 4%, or 5% to 3%).

The numbers sought have been inflated to 6,500 to take account of losses to followup. The main reason for 'loss to follow up' will be death. In the large Dutch trial¹² the rate was about 20% over three years, but we expect it to be higher overall (about 30%) because some of our participants will have sustained a recent proximal femoral fracture. Losses for other reasons, principally moving to other areas, are estimated from observations in one participating centre to be about 5%. The sample size has therefore been inflated by 35%.

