6. ANALYSIS PLANS

6.1 Ground rules for the statistical analyses

The statistical analyses will be based on all people randomised, irrespective of subsequent compliance with pill taking. The principal comparisons will be:

- (i) all those randomised vitamin D versus all those not allocated vitamin D
- (ii) all those randomised calcium versus all those not allocated calcium
- (iii) all randomised vitamin D and calcium versus all randomised Vitamin D alone versus all randomised calcium alone versus all randomised placebo

Evidence will be sought for an interaction between vitamin D and calcium.

The analyses will be based on two denominators:

- (i) all participants with data irrespective of length of follow-up, using 'time to an event' and multidecrement life-table analysis techniques
- (ii) all those with follow-up to 24 months

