6.2 Measures of outcome

The principal clinical outcome measure is:

• all new low-energy fractures (other than face or skull) or clinical, radiologicallysupported, vertebral fractures reported.

Any apparent differences in fracture rates will be explored by subdivision into: proximal femoral, other lower limb/pelvis, distal forearm, other arm, clinical vertebral, and other fractures.

Other secondary outcome measures are:

- New radiologically-confirmed fractures
- Death after trial entry; the possible link between death and fracture will be examined in analyses of deaths occurring within three months of a new fracture
- General health status as measured by SF-12 and EQ-5D
- Hospital admissions after trial entry (number, length, place, and association with fracture)
- Change of residence category
- Falls (within five one-week window periods)
- Possible adverse effects (e.g. renal stones, gastrointestinal symptoms)
- New cancer registrations (Total, colon, breast, other)
- Deaths attributed to cardiovascular or cerebrovascular disease
- New cases of diabetes, taking oral hypoglycaemics and/or insulin

The ways in which these data will be displayed in the final report are illustrated in Appendix 11.

It is anticipated that other variables, such as bone density, genetic polymorphisms, and balance will be measured in explanatory studies and these will be described in separate protocols.

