6.4 Secondary sub-group analyses

Sub-group analyses similar to the principal analyses will be performed after stratification by (a) the type of fracture sustained prior to trial entry (proximal femur, distal forearm, clinical vertebral, or other), (b) age at entry (70-74, 75-79, 80-84 and 85 or over), (c) sex, (d) latitude of recruitment centre (northern versus central versus southern), (e) time of enrolling fracture (within 3 months of recruitment or longer), (f) dietary calcium (high or low) and vitamin D exposure (high or low), (g) high or low weight (less than 55kg or not), and (h) level of compliance (completed two years or not). The Chi-squared test for heterogeneity will be used to explore any apparent differential effects. The principal outcome will be subdivided into categories of fracture, again to explore possible differential effects. Stricter levels of statistical significance (2P<0.01) will be sought, reflecting the exploratory nature of all these analyses.

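### The hip fracture power in section 7.1 holds at 2P<0.05, but section 6.4, read literally, judges fracture categories at 2P<0.01, where power is about 63% and 74%

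*Protocol*

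**What the plan says.** Three sections of the protocol bear on hip fracture.

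- **Section 7.1 (Sample size sought)** sizes the trial on all fractures: 15% against 12%, 80% power, 2P<0.05, 4,000 in the analysis. It then adds: "A trial of this size also has over 80% power to identify a 2% absolute difference in hip fracture rates", giving 6% to 4% and 5% to 3% as the cases. The hip sentence has no significance level of its own; the only one in that paragraph is 2P<0.05.
- **Section 6.2 (Measures of outcome)** does not list hip fracture among its bulleted outcomes. It appears as a category of the principal outcome: "Any apparent differences in fracture rates will be explored by subdivision into: proximal femoral", followed by the other fracture sites.
- **Section 6.4 (Secondary sub-group analyses)** first lists the participant sub-groups, then says that the principal outcome will also be split by fracture category, again for exploration. The next sentence sets the threshold: "Stricter levels of statistical significance (2P<0.01) will be sought, reflecting the exploratory nature of all these analyses".

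No section exempts hip fracture from that threshold.

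**The concern.** A power figure describes a test at a stated significance level. Here the power is quoted at one level, while the plan appears to judge the same comparison at a stricter one.

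Two things follow. First, a reader of section 7.1 would take the chance of missing a true two-point reduction to be below 20%; at the section 6.4 threshold it is larger. A hip result that misses the threshold could then be over-read as evidence against benefit. Second, a hip result with P between 0.01 and 0.05 could be called positive by the standard of section 7.1 and inconclusive by that of section 6.4. That choice should not be left open until the data are known. Hip fracture is the only fracture type with its own power statement, so the result is likely to be looked for.

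**Working it through.** **Inputs.** From section 7.1: 4,000 analysed; hip rates 6% v 4% and 5% v 3%; 6,500 recruited; 35% expected losses (30% deaths, 5% other). From section 6.1: the comparison is of factorial margins, such as "all those randomised vitamin D versus all those not allocated vitamin D". Equal allocation to the four groups is assumed, since no ratio is stated; this gives n = 2,000 per side. Two-sided critical values are 1.960 at 0.05 and 2.576 at 0.01.

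**Step 1: check the basis.** For 15% v 12% with 2,000 per side, power at 0.05 is 79.3%, and 80% needs 4,072 in total. This agrees with the stated 4,000 to within 2%, so 2,000 per side is the right reading of the section.

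**Step 2: reproduce the hip figure at 0.05.** Formula: z = d / √[(p₁(1−p₁) + p₂(1−p₂)) / n], power = Φ(z − critical value).

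- 6% v 4%: z = 0.02 / √[(0.0564 + 0.0384)/2000] = 2.905; Φ(2.905 − 1.960) = 82.8%.
- 5% v 3%: z = 0.02 / √[(0.0475 + 0.0291)/2000] = 3.232; Φ(3.232 − 1.960) = 89.8%.

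Both exceed 80%, so the stated figure is reproduced.

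**Step 3: the same comparison at 0.01.**

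- 6% v 4%: Φ(2.905 − 2.576) = 62.9%.
- 5% v 3%: Φ(3.232 − 2.576) = 74.4%.

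The choice of approximation matters little. A pooled variance gives 62.8% and 74.3%, the arcsine method 63.3% and 75.1%, and a continuity correction 60.0% and 71.6%.

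**Step 4: vary the number analysed, at 0.01.**

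| Analysed | Basis | 6% v 4% | 5% v 3% |
|---|---|---|---|
| 4,000 | section 7.1 | 62.9% | 74.4% |
| 4,225 | 6,500 × 0.65 | 65.9% | 77.2% |
| about 5,360 | 6,500 × (0.65 + 0.35/2); assumes losses spread evenly over follow-up | about 78% | about 88% |
| 6,500 | no losses | 87.0% | 93.9% |

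For 80% power at 2P<0.01 the totals are 5,546 (6% v 4%) and 4,482 (5% v 3%), against 3,726 and 3,012 at 2P<0.05 (pooled variance).

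**The case against.** **It is not a miscalculation.** This stands. At the only significance level in its paragraph, the hip statement is right. A reader who sees 63% beside a claim of more than 80% might infer an arithmetic slip; step 2 shows there is none.

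**Hip fracture may already be a secondary outcome.** After naming the fracture categories, section 6.2 introduces its bulleted list with the word *Other* before *secondary*. That can be read as making the categories secondary outcomes too, with no 2P<0.01 rule attached in that section. This leaves some real doubt about the status of hip fracture. Against it, the same section describes the subdivision as exploration of apparent differences.

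**The stricter threshold may concern only heterogeneity.** Section 6.4 is headed as sub-group analysis and names a chi-squared test for heterogeneity, so the threshold might govern only whether effects differ between groups or fracture types. Its wording is also soft: stricter levels are to be *sought*. But the sentence on fracture categories comes immediately before the threshold, and the threshold is applied to *all* the analyses described. The literal reading therefore includes the categories, although the text could be plainer.

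**63% and 74% are at the low end.** This is partly right. Section 6.1 includes a time-to-event analysis of everyone with data, so people who die or are lost contribute until they leave. Under the even-loss assumption, power at 0.01 rises to about 78% and 88%. But section 7.1 makes its own claim on 4,000 analysed, and on that basis the lower figures are the like-for-like ones.

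**Conclusion.** The inconsistency is real and of moderate importance. On section 7.1's own basis, power for hip fracture is about 83% and 90% at 2P<0.05 but about 63% and 74% at the 2P<0.01 that section 6.4 literally applies to fracture categories. At the stricter level a true fall from 6% to 4% would be missed about 37% of the time (100 − 62.9), and a fall from 5% to 3% about 26% of the time (100 − 74.4).

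This rests on three readings: that the trial size in the hip sentence means the 4,000 analysed, that allocation is equal, and that the section 6.4 threshold covers the comparison of treatments within each fracture category. The first is well supported by the preceding sentences and by step 1; the second is an assumption; the third is the literal sense but not beyond doubt.

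A reader might go further and infer that the trial is too small or that recruitment should rise towards the totals for 80% power at 2P<0.01. The protocol does not support that. The sample size rests on the principal outcome at 2P<0.05, the hip sentence is an additional remark, and neither the principal comparisons nor recruitment depends on it.

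**What to change.** Keep the 2P<0.01 rule and restate the hip sentence in section 7.1 with its significance level, for example: about 63% power (6% to 4%) and 74% power (5% to 3%) at the 2P<0.01 level of section 6.4, with 4,000 analysed; 83% and 90% at 2P<0.05. If the sponsor prefers to credit partial follow-up, the assumed pattern of losses should be stated with the resulting figure.

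If hip fracture was intended as a secondary outcome outside the section 6.4 threshold, then sections 6.2 and 6.4 must both say so before any unblinded data are seen. That would make the present power sentence true, but by relaxing an error control that the protocol has set for its exploratory analyses. It is a trade-off for the sponsor to decide and justify, not a mere correction.

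Either change takes a sentence or two and alters neither sample size nor conduct. The cost of the first is that a stated power becomes less favourable; the cost of the second is a weaker threshold for one fracture category.

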7.2 Recruitment rates

The aim is to recruit an average of 65 participants per week over a two-year period. Recruitment will be primarily from out-patient clinics and inpatient fracture units, although additional patients may also be identified from medical records as having sustained an eligible fracture in the preceding two years. It is expected that 50% of eligible patients will agree to participate and so 6500 will need to be approached per year. In the United Kingdom, a centre serving a population of 500,000 would expect approximately 750 eligible new fracture attendances each year, of whom around a third will have sustained a proximal femoral fracture. Taking into account that some centres will be smaller, the trial will have about 15 centres recruiting at rates between 2 and 5 per week.

8. ORGANISATION

8.1 Local organisation

- Each collaborating centre will identify a *clinical co-ordinator*. The responsibilities of this person will be to:
 - 1. establish the trial locally (for example, by getting agreement from clinical colleagues, facilitating local research ethics committee approval; identifying and appointing a local study nurse; and ensuring that all clinical staff involved in the care of people with fractures are informed about the trial)
 - 2. take responsibility for clinical aspects of the trial locally (for example, if any particular concerns emerge)
 - 3. notify the Trial Office of any unexpected clinical events which might be related to trial participation
 - 4. provide support and supervision for the local study nurse
 - 5. represent the centre at collaborators meetings

- Each clinical centre will appoint a *study nurse* to co-ordinate the day to day aspects of the trial. The responsibilities of this person will be to:
 - 1. keep local staff informed of progress in the trial
 - 2. keep regular contact with the local clinical co-ordinator, with notification of any problem or unexpected development
 - 3. to maintain regular contact with the Trial Office
 - 4. identify potential participants and keep a log of whether or not they are recruited (with reasons for non-participation)
 - 5. check eligibility, give information about the trial, and seek consent
 - 6. collect baseline data describing participants, and send these to the Trial Office
 - 7. supply initial materials to patients, if applicable
 - 8. telephone each person recruited two weeks after trial entry to check all is well and subsequently when judged necessary
 - 9. clarify the situation when the Trial Office fails to make a contact with a local participant, getting in touch by phone or a visit, if necessary
 - 10. seek further clinical details when a major trial event (such as a fracture or death) is reported to the Trial Office, even if this occurs in another hospital
 - 11. assist in the conduct of explanatory studies, if applicable
 - 12. provide support for participants in other ways if there are difficulties
 - 13. represent the centre at trial nurse meetings and collaborators meetings

8.2 Trial co-ordination

• The Trial Office

The Trial Office is in the Health Services Research Unit at Aberdeen and gives day to day support to the clinical centres. It is responsible for collection of data (in collaboration with the local study nurses), data processing and analysis. It is also responsible for randomisation, despatch of trial materials to participants, and unblinding, as clinically necessary.

• The Project Management Group

The trial is co-ordinated by its Project Management Group. This consists of representatives from six of the clinical centres, and representatives from the Trial Office. Observers may be invited to attend at the discretion of the Project Management Group.

• The Steering Committee

The trial is supervised by an MRC Steering Committee. This is made up of three independent members selected by the MRC, together with those originally granted funds to mount the trial. Observers from the MRC and host university (University of Aberdeen) may also attend. Other members of the Project Management Group may attend as observers at the invitation of the Chair of the Steering Committee.

8.3 Data and safety monitoring

• The Data Monitoring Committee

A data monitoring committee will be established. This will be independent of the trial organisers. During the period of recruitment to the trial, interim analyses will be supplied, in strict confidence, to the data monitoring committee, together with any other analyses that the committee may request. This may include analyses of data from other comparable trials. In the light of these interim analyses, the data monitoring committee will advise the Steering Committee if, in its view, one or more of the randomised comparisons in the trial has provided both (a) proof beyond reasonable doubt¹ that for all or some types of patients one particular type of intervention is clearly indicated in terms of a net reduction in fracture risk without any increased risk of death (or clearly contraindicated because of a net increase in fracture risk or mortality), and (b) evidence that might reasonably be expected to influence materially the care of people who sustain a fracture by clinicians who know the results of this and comparable trials. The Steering Committee can then decide whether or not to modify intake to the trial. Unless this happens, however, the steering committee, project management group, clinical collaborators, and trial office staff (except those who supply the confidential analyses) will remain ignorant of the interim results.

Note:

¹ Appropriate criteria for proof beyond reasonable doubt cannot be specified precisely. A difference of at least three standard deviations in the interim analysis of a major endpoint may be needed to justify halting, or modifying, such a study prematurely. If this criteria were to be adopted, it would have the practical advantage that the exact number of interim analyses would be of little importance, and so no fixed schedule is proposed (Peto R et al *Br J Cancer* 1976; 34: 584-612).

The frequency of interim analyses will depend on the judgement of the chairman of the committee, in consultation with the Steering Committee. Initially, the principal concern will be possible adverse effects. Data on new fractures will accumulate slowly so the committee is unlikely to be able to consider these reliably until some way into the trial.

Other safety concerns

The incidence of adverse effects from the proposed dosage of vitamin D and calcium is anticipated to be very low - in the systematic review renal insufficiency or stones were reported for 4/4025 (0.1%) and gastro-intestinal disturbances for 93/3892 (2.4%).

Collaborators and participants may write to the chairman of the steering committee about any worries they may have about the trial. If concerns arise about particular side-effects or about particular types of participants, these will be relayed to the Chairman of the Data Monitoring Committee.

If clinically indicated, rapid unblinding of trial materials will be available through the trial office.

The Multicentre Research Ethics Committee for Scotland has approved the trial. The trial will be conducted according to the MRC Good Clinical Practice Guidelines (1998)²².

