5. DATA COLLECTION AND PROCESSING

Follow-up will continue for a median period of three years (range two to four years). Although further follow-up is anticipated, this is not part of this protocol.

Data from the various sources outlined above will be sent to the Trial Office in Aberdeen for processing. Staff in Aberdeen will work closely with study nurses to secure as complete and accurate data as possible. A random 10% sample of data will be double-entered to check accuracy. Extensive range and consistency checks will further enhance the quality of the data.

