6.3 Timing and frequency of analyses

A single principal analysis is anticipated two years after the last person is recruited. If considered appropriate, follow-up of recruits will be extended at this time. The data and safety monitoring committee (see below) will determine the frequency of confidential interim analyses.

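### Section 8.3 states interim analyses for the recruitment period and a response on intake only, although, with uniform accrual, about 62% to 67% of follow-up comes after recruitment closes

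*Protocol*

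**What the plan says.** **Monitoring (Protocol 8.3).** The period for supplying comparative data is given in one sentence: "During the period of recruitment to the trial, interim analyses will be supplied, in strict confidence, to the data monitoring committee". The committee's right to ask for other analyses is in the same sentence, after the same opening phrase. If the committee reports convincing evidence of benefit or harm, the text continues: "The Steering Committee can then decide whether or not to modify intake to the trial". The section also says: "Data on new fractures will accumulate slowly so the committee is unlikely to be able to consider these reliably until some way into the trial". A footnote discusses a possible criterion: "A difference of at least three standard deviations in the interim analysis of a major endpoint may be needed", to justify halting or modifying a study early. It proposes no fixed schedule.

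**Timetable.** Section 7.2: "The aim is to recruit an average of 65 participants per week over a two-year period". Section 6.3: "A single principal analysis is anticipated two years after the last person is recruited". Section 5 gives a median follow-up of three years, with a range of two to four. Section 3.4 has tablets posted to all participants every four months and states no earlier end to supply, so I read treatment as continuing through follow-up.

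**Frequency.** Section 6.3 says that the committee "will determine the frequency of confidential interim analyses" and gives no period.

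**The concern.** The stated window and the stated response suit a trial in which treatment is short and most exposure falls within recruitment. Here treatment lasts two to four years. For the last two of the four calendar years nobody is being recruited, so there is no intake to modify, while those still in follow-up continue to be sent tablets.

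The participants are aged 70 or over. Section 8.3 itself allows for an intervention proving contraindicated because fracture risk or mortality rises. The natural response to that finding after recruitment closes is to stop the tablets concerned, and no sentence names that step. An excess that emerged only with longer use would have no stated comparison by arm before the principal analysis. The DMC could advise, but the decision to act belongs to the Steering Committee.

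**Working it through.** **Inputs**
- Recruitment: 6,500 people (7.1) over two years (7.2).
- Principal analysis: two years after the last recruit (6.3), so year 4 from the start.
- Losses: about 30% deaths plus 5% other (7.1). I read these as 35% over three years, because the cited Dutch rate is given over three years.
- Assumptions of mine: uniform accrual and a constant loss hazard.

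**1. Reproduce the stated follow-up.** Let u be the time from a participant's entry to the close of recruitment, uniform on 0 to 2 years. Follow-up to the principal analysis is u + 2, which has median 3 and range 2 to 4, as section 5 states.

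**2. No losses.** Mean follow-up per person is 1.0 year before closure and 3.0 years in all. Person-years: 6,500 × 1.0 = 6,500 of 6,500 × 3.0 = 19,500. Share after closure: 1 − 6,500/19,500 = **66.7%**.

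**3. With 35% loss over three years.**
- Loss hazard h = −ln(0.65)/3 = 0.1436 per year.
- Mean proportion still in follow-up at closure: (1 − e^(−2h))/(2h) = 0.869. Number: 6,500 × 0.869 ≈ **5,650**.
- Mean follow-up before closure: (1 − 0.869)/h = 0.911 years.
- Mean follow-up in all: (1 − e^(−2h) × 0.869)/h = (1 − 0.7504 × 0.869)/0.1436 = 2.422 years.
- Person-years: about 5,920 of 15,740. Share after closure: 1 − 0.911/2.422 = **62.4%**.

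**4. Sensitivity.**

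| Accrual over two years | No loss | 35% loss over three years |
|---|---|---|
| Uniform | 66.7% | 62.4% |
| Rising linearly | 75.0% | 71.8% |
| Falling linearly | 60.0% | 54.5% |

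More than half of follow-up comes after closure in every case.

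**5. Fractures follow the same pattern.** Take the 15% control rate (7.1) as a constant hazard over three years in all participants. With 35% loss, about 310 of 790 first fractures (39%) occur before closure, so about 61% come later. With no loss, about 65% come later.

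**6. What later looks cost in type I error.** Assume yearly looks at three standard deviations and an unadjusted final test at 1.96, in simulation. The two-sided error is about 5.4% with looks at years 1 and 2, and still about 5.4% with year 3 added. With half-yearly looks it is about 5.7% to year 2 and 5.8% to year 3.5. This agrees with the footnote's remark that the number of analyses would matter little under such a criterion.

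**The case against.** **Saying when analyses are supplied does not say that they stop.** This stands. A reader might infer that comparative review must end when recruitment closes; the documents do not support that. Section 6.3 leaves frequency to the committee with no end date, and 8.3 leaves it to the chairman's judgement in consultation with the Steering Committee. A chairman who asked for a report in year 3 would breach nothing. The defect is that the only stated period is too short, and frequency is not duration.

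**Action is not confined to intake.** This stands in part. The footnote mentions halting or modifying a study, the Steering Committee supervises the whole trial (8.2), and the sentence on intake is permissive. But the footnote discusses a threshold, and the sentence that states the decision names intake alone.

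**There are other safety routes.** Section 8.3, under other safety concerns, relays worries about side effects to the DMC chairman and provides rapid unblinding. General practitioners report events (4.5), nurses search for fractures and deaths during follow-up (4.7), and deaths and cancers are flagged (4.8). These have no recruitment limit. They bring in individual events, however, and cannot show an excess in one arm unless someone compares the arms.

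**The text does not contradict itself.** This also stands. A reader might see a conflict between the recruitment window and the remark that fractures cannot be judged reliably until some way in, or between 8.3 and 6.3. That point could fall within two years, and 6.3 deals with frequency rather than period. The passages fit together poorly but do not conflict.

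**A committee charter may cover this.** It may, and it is not in the documents. The protocol would still carry the narrower wording.

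**Conclusion.** The point holds as a matter of badly fitting wording, worth correcting but not a serious flaw. For the two years after recruitment closes, the protocol states no comparison by arm and no action on continued treatment. That period holds about 62% to 67% of follow-up under uniform accrual, or roughly 55% to 75% with falling or rising accrual, and begins with about 5,650 people still in follow-up (more with lighter losses). The figures rest on the planned two-year recruitment, a constant loss hazard, and the 35% loss read as over three years.

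Two stronger readings should not be drawn. The protocol does not forbid later monitoring. Nor can one put a firm number on the chance of missing an early stop: that would need a look schedule, which the protocol does not set, and three standard deviations as a rule, which the footnote only suggests.

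**What to change.** Change two phrases in section 8.3:
- Replace the opening of the supply sentence with: *During recruitment and follow-up, until the principal analysis, interim analyses will be supplied…*
- Extend the Steering Committee's decision to: *modify intake to, or continued allocated treatment in, the trial*.

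Leave frequency and thresholds to the committee's judgement, as now. Design and sample size do not change.

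The cost is one or more further confidential reports, built from data that the four-monthly forms and the other notification routes already bring in.
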